An Observational Study of Beta-Blocker Use in Patients with Chronic Obstructive Pulmonary Disease (COPD) and Acute Myocardial Infarction

Version 4.0

May 20, 2020

1. Introduction

Chronic obstructive pulmonary disease (COPD) is the third leading cause of death worldwide and a major contributor to morbidity and mortality is comorbid cardiovascular disease. COPD is an independent risk factor for coronary artery disease and myocardial infarction (MI) is a common cause of death in those with the disease. Beta-blockers have been demonstrated to reduce the risk of death and reinfarction after MI and though observational studies suggest that this benefit extends to patients with COPD, this has not been definitively proven in randomized controlled trials. Results of the recently published randomized, placebo-controlled trial, Metoprolol for the Prevention of Acute Exacerbations of COPD (BLOCK COPD), demonstrate that beta-blockers do not reduce the risk of COPD exacerbations and increase the risk of exacerbations requiring hospitalization raising questions about the overall risk-benefit of the drugs in COPD patients, including those with class I indications such as MI. We propose a multicenter, observational study to examine the association between beta-blocker use and all-cause mortality and hospitalization following MI in patients with COPD.

2. Background

Results and Clinical Implications of the BLOCK COPD Trial

Chronic obstructive pulmonary disease (COPD) is the third leading cause of death worldwide and the majority of COPD-related morbidity, mortality and healthcare costs are driven by exacerbations, particularly those requiring hospitalization (1, 2). Possible explanations for the failure of existing treatments to control exacerbations adequately include the fact that events may be triggered or made more severe by underlying cardiovascular disease(3). Compared to age-matched controls, COPD is associated with up to a 5-fold risk of cardiovascular disease(4) which is a risk factor for exacerbation (5), hospitalization for exacerbation (6), in-hospital mortality (7, 8), and reduced survival (9, 10).

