It is well established that beta-blockers reduce mortality in patients after myocardial infarction(11) and in the presence of heart failure.(12) Patients with COPD are often denied this class of medications, even in the presence of evidence based indications for their use, because of concerns about possible adverse effects on lung function.(13, 14) This practice pattern persists despite multiple observational studies suggesting beta-blockers benefit patients with COPD and comorbid cardiovascular disease with outcomes comparable to those observed in patients without COPD (13, 15, 16). Recent non-randomized studies also suggest that beta-blockers reduce the risk of exacerbations and mortality in patients with COPD, with or without known cardiac disease.(17-20) However, these observational data are subject to biases, precluding conclusions about cause and effect (21).

To address these issues, we investigated the effect of metoprolol on the risk of exacerbations in COPD patients at high risk for those events (ClinicalTrials.gov number: NCT02587351) (22, 23). We hypothesized that metoprolol would reduce the risk of exacerbations compared with placebo and would not adversely impact lung function, six-minute walk distance, dyspnea, or quality of life.

We randomized 532 participants with a mean (\pm SD) age of 65.0 ± 7.8 years and FEV₁ of 41.1 ± 16.3 % predicted. The study was stopped early due to futility for the primary endpoint and safety concerns. There was no difference in time to first exacerbation between groups and the hazard ratio (HR) for assignment to metoprolol was 1.05 (95%CI: 0.84-1.32; p=0.66). Metoprolol was associated with a higher risk of exacerbation requiring hospitalization (HR 1.91, 95%CI: 1.29-2.83). Patient reported possible beta-blocker side effects were similar between groups as was

the overall rate of non-respiratory serious adverse events. During the treatment period, we observed 11 deaths in the metoprolol group and 5 in the placebo group.

The results of the study strongly indicate that patients with COPD and at risk for exacerbation should not be prescribed beta-blockers in the absence of an established indication for the drugs such as recent myocardial infarction or heart failure.

Unanswered Questions and the Rationale for the Proposed Study

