Patients admitted to the hospital and who undergo cardiac catheterization for an AMI will be identified through the electronic medical record (EMR). Those with a diagnosis of COPD in the EMR will be offered participation in the study. Baseline characterization will include demographics, smoking history, prior history of exacerbations in the year before admission, supplemental oxygen use, respiratory and cardiac medication use, comorbidities including history of coronary artery disease, heart failure and ejection fraction, and pulmonary function data as available in the EMR. Results of this Aim will provide data about the prevalence and clinical characteristics of COPD in the hospitalized population with AMI in our network. The Aim will also provide an estimate of the number of annual admissions for patients with COPD and AMI.

Specific Aim 2. To determine the association between beta-blocker use at discharge and cardiopulmonary outcomes in patients with COPD and AMI.

Patients with AMI and EMR-documented COPD will be followed, prospectively from the time of discharge using review of the electronic medical record and as local guidance permits, phone calls at 3 and 6 months. We will determine the associations between beta-blocker use at discharge and the risk for all-cause mortality, recurrent ischemic events, and hospitalization for COPD exacerbation adjusting for baseline characteristics and COPD severity.

4. Study Design and Methods

- a) **Overview.** The study is a prospective, observational study of patients admitted to the BLOCK COPD network hospitals with acute AMI and COPD. Patients with will be identified via the EMR. Because of the current COVID-19 pandemic and the possibility of limited access to hospitalized patients, the study consists of three options for enrollment. Option 1 or 2 is preferable if local guidance permits.

Option 1: A total of 3 visits including 1 in person visit in the hospital and 2 follow up phone calls with EMR review at 3 and 6 months after discharge. Sites may consider alternatives to in person consent and data collection including by telephone or video conference.

Option 2: EMR review at the time of hospital admission followed by post-discharge telephone consent and 2 follow up phone calls with EMR review at 3 and 6 months.

Option 3: EMR review at the time of hospital admission and follow-up review of the EMR at 3 and 6 months after discharge.

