- a. Analysis plan for Aim 1. The primary objectives of Aim 1 are to determine the number of admissions per year for AMI at our participating institutions and the prevalence of COPD in that population. These prevalence estimates will be calculated as a simple fraction. We will also compare the clinical characteristics of COPD patients discharged on a beta-blocker versus those not discharged on a beta-blocker using t-tests or chi-square tests (or Fisher's exact tests) as appropriate.
- b. Analysis plan for Aim 2. For the primary analysis we will compare the risk of death or all-cause hospitalization at 6 months for patients with AMI and COPD who were discharged alive on beta-blockers to that of patients not

discharged on beta-blockers. Secondary analyses will include comparisons of rates of hospitalization for COPD exacerbations, rates of hospitalization for recurrent MI or revascularization or heart failure, and rates of treatment with steroids and/or antibiotics for exacerbations. The primary analysis will be based on adjusted Kaplan–Meier survival curves that describe the probability remaining alive and out of hospital in those discharged versus not discharged on beta-blockers, while adjusting for the inverse probability of treatment weighting (IPTW) to reduce confounding. For all time-to-event analyses, the start time will be when the participant is discharged from the hospital.

Participants will be censored at 6 months post-discharge if no event occurred. The comparison of clinical characteristics between treatment groups conducted in aim 1 will be used to inform the calculation of the IPTW. We will use the adjusted log-rank test to compare the two curves. As secondary analyses, we will use both IPTW and adjusted Cox proportional-hazards models to assess the association between the beta-blocker prescription and death or re-hospitalization. Adjusted models will also include the covariates of race, sex, baseline age, smoking status, number of hospitalizations for COPD during the previous year, use of supplemental oxygen, presence of ejection fraction <40% at discharge. Assuming adequate frequencies between groups, we will stratify the models by beta-blocker use at the time of admission, presence of asthma, STEMI vs. NSTEMI, and site. Rates of exacerbation will be analyzed by IPTW negative binomial regression models and will be used to compare annualized rates of hospitalization.

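### Aim 2 names all-cause mortality first among its outcomes, but the Aim 2 analysis plan specifies no analysis with death alone as the endpoint

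*Combined protocol and SAP*

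**What the plan says.** **The aim.** The Introduction (section 1) says the study will "examine the association between beta-blocker use and all-cause mortality and hospitalization following MI in patients with COPD". Specific Aim 2 (section 3) will determine "associations between beta-blocker use at discharge and the risk for all-cause mortality, recurrent ischemic events, and hospitalization for COPD exacerbation", and section 7.c repeats this. These are three separate outcomes, with mortality first.

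**The analysis.** In section 4.g.b the primary comparison is on a composite: "we will compare the risk of death or all-cause hospitalization at 6 months for patients with AMI and COPD". The weighted Kaplan–Meier curves "describe the probability remaining alive and out of hospital in those discharged versus not discharged on beta-blockers", so each patient contributes only the first event. The Cox models, weighted and covariate-adjusted, are there "to assess the association between the beta-blocker prescription and death or re-hospitalization". The other endpoints are introduced with "Secondary analyses will include comparisons of rates of hospitalization for COPD exacerbations, rates of hospitalization for recurrent MI or revascularization or heart failure", followed by steroid and antibiotic treatment for exacerbations.

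**The data.** Section 4.f.b collects vital status and the date and cause of death at 3 and 6 months. Nothing there stops collection at a readmission.

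**The concern.** The other two Aim 2 outcomes each have a counterpart among the secondary analyses. Mortality does not. A statistician following section 4.g.b to the letter would produce no mortality curve, mortality difference or mortality hazard ratio. A patient readmitted in month 1 who dies in month 4 would be counted as a readmission.

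The study is meant to inform the overall risk-benefit of beta-blockers after infarction in COPD, and death is the gravest part of that balance. This is also a confounded comparison adjusted by weighting. A mortality analysis whose endpoint and method are chosen after the data are seen would carry less weight than one fixed in advance.

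**Working it through.** **1. Aim against analysis**

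| Aim 2 outcome (section 3) | Analysis in section 4.g.b |
|---|---|
| All-cause mortality | None alone; only within the composite |
| Recurrent ischemic events | Hospitalization for MI, revascularization or heart failure |
| COPD hospitalization | Hospitalization for COPD exacerbation |

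**2. Is the Cox endpoint one composite or two endpoints?** Section 4.g.c uses the same phrase for a single risk: 25% on beta-blockers against 32.5–37.5% without. Table 1 reproduces on that reading. With 37.5% against 25%, 65% on beta-blockers, two-sided 5% and 80% power:
- HR = ln(0.75)/ln(0.625) = 0.612
- Events (Schoenfeld) = (1.960 + 0.842)² / [0.65 × 0.35 × (ln 0.612)²] = 143.2
- N = 143.2 / (0.65 × 0.25 + 0.35 × 0.375) = 143.2/0.29375 = 487.4, rounded up to 488, as printed

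All 44 cells match in this way. The phrase denotes one composite, and mortality has no sizing of its own.

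**3. Deaths after a first readmission.** The documents do not give this share, so a model is needed. Inputs:
- Composite risk without beta-blockers, p = 32.5–37.5% (section 4.g.c)
- Assumed: constant hazards over 6 months
- Assumed: deaths as a share of first events, d = 10–30%
- Assumed: death hazard after readmission k times that before, k = 1 or 3

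Let L = −ln(1 − p), and let m = k·d·L be the 6-month cumulative death hazard after readmission.
- Deaths as first event: d·p
- Deaths after readmission: (1 − d)·L·[p/L − (e^−m − e^−L)/(L − m)]

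Example with p = 0.375, d = 0.10, k = 3: L = 0.470 and m = 0.141. First-event deaths are 0.0375 and later deaths 0.02444, so the share is 0.02444/0.06194 = 39.5%.

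| p | d | Share, k = 1 | Share, k = 3 |
|---|---|---|---|
| 32.5% | 10% | 15.7% | 35.2% |
| 32.5% | 30% | 12.3% | 28.1% |
| 37.5% | 10% | 18.3% | 39.5% |
| 37.5% | 30% | 14.5% | 31.6% |

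The ranges are about 12–18% and 28–40%. For the beta-blocker group, at its assumed risk of 25%, the same formulas give 9.3–11.8% and 22.5–28.3%.

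**4. What the composite can say about death.** To a first approximation, composite HR = d × HR(death) + (1 − d) × HR(hospitalization). Setting it to 1 with a death HR of 0.60, the hospitalization HR that offsets it is 1 + 0.40d/(1 − d): 1.04 at d = 10% and 1.17 at d = 30%. This illustrates sensitivity and is not a forecast.

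**5. Precision of a mortality analysis.** Section 4.g.c gives 1-year mortality of 14–25%. Assuming a constant hazard and applying it to patients without beta-blockers, 6-month mortality is 1 − √0.86 = 7.3% to 1 − √0.75 = 13.4%. With N = 500, 45–85% on beta-blockers and the cited mortality reductions of 9–50%, expected deaths are:
- Lowest: 500 × 0.0726 × (0.85 × 0.50 + 0.15) = 21
- Highest: 500 × 0.1340 × (0.45 × 0.91 + 0.55) = 64

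The 95% limits lie a factor exp[1.96/√(D·q(1 − q))] either side of the HR, where D is deaths and q the proportion on beta-blockers:
- D = 50, q = 0.70: exp(1.96/√10.5) = 1.83
- D = 21, q = 0.85: exp(1.96/√2.68) = 3.3

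Weighting will widen these. Power to detect a 40% mortality reduction is about 15–51%.

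**The case against.** **The gap is one of specification.** Aim 2 commits to a mortality association, the data are collected, and section 4.g.b introduces its secondary analyses as a list that need not be closed. A reader might infer that the mortality question cannot be answered at all. The documents do not support that: the analysis could be run. What stands is that no endpoint definition, method or place in the hierarchy is given for it.

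**Part of any cancellation would be seen.** A reader might infer that a null composite could not be told apart from fewer deaths with more COPD admissions. But COPD and cardiac admissions are separate secondary analyses, so that side would show. Only the death side is hidden.

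**The background does not predict cancellation.** It is tempting to pair the mortality relative risks of 0.60 and 0.85 in section 2 with the parent trial's hazard ratio of 1.91 for hospitalized exacerbation. These come from different populations. The 0.85 applies to COPD patients without beta-agonists, recent oral steroids or a recent COPD admission; the same study found no benefit in those treated with beta-agonists or for acute symptoms in the prior year. The parent trial had 11 deaths on metoprolol and 5 on placebo, which is not an opposing benefit. Section 4.g.c itself assumes a net fall in the composite. Opposite effects are possible, but the plan does not expect them.

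**The composite is a reasonable primary at this size.** With about 21–64 deaths, mortality could not carry the primary analysis. That stands, and it argues for a secondary estimate with an interval rather than for none.

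**Conclusion.** The mismatch holds on the text alone and needs no modelling: Aim 2's first-named outcome has no specified analysis.

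The size of the loss rests on assumptions. The event shares, constant hazards and the tripling are illustrative. Using the documents' own 1-year mortality under constant hazard, with no change after readmission, deaths would be 0.0754/0.470 = 16% to 0.1438/0.393 = 37% of first events. The share of deaths after readmission is then 1 − d·p divided by 6-month mortality: 17% (1 − 0.0602/0.0726) to 11% (1 − 0.1189/0.1340). So more than a tenth of deaths in patients without beta-blockers is a fair lower figure, and the share rises well above that if readmission marks higher risk.

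The point is worth correcting because the remedy is cheap and lets the study report on its own stated aim. It does not invalidate the primary analysis.

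**What to change.** In section 4.g.b:
- Keep the composite as the single primary contrast.
- Add all-cause mortality to 6 months after discharge as a named secondary endpoint, counting every death, including those after a readmission, from the vital-status data in section 4.f.b.
- Use the planned weighted Kaplan–Meier and Cox methods, and report the 6-month risk difference and the hazard ratio with 95% confidence intervals.
- State that a null composite is not evidence of no effect on mortality, and that the mortality result is mainly descriptive.

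The cost is a few sentences and one more run of the planned analysis, with no new patients, visits or data items. The drawback is the imprecision shown above: an interval that includes 1 will probably also include clinically important benefit or harm, and the report should say so.

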 - iii. COPD assessment - year of diagnosis, home use of supplemental oxygen, self-reported history of spirometry being conducted, number of hospitalizations for COPD exacerbations in the year prior to admission, number of courses of antibiotics and/or steroids for COPD exacerbations in the year prior to admission. For protocol Option 1 this will be collected via self-report utilizing a questionnaire during the hospitalization. For protocol Option 2, this information will be obtained

after discharge and phone consent. For protocol Option 3 as much of this information as possible will be collected from review of the EMR.

- iv. Most recent forced expiratory volume (FEV1) and forced vital capacity (absolute and percent predicted) from EMR if documented in the 3 years prior to admission
- v. Comorbidity assessment to include cardiovascular disease and risk: history of hypertension, hyperlipidemia, coronary artery disease, prior MI, heart failure (ejection fraction prior to admission if available), percutaneous coronary intervention (PCI), coronary artery bypass grafting (CABG), peripheral vascular disease, stroke, diabetes mellitus, cirrhosis, asthma, obstructive sleep apnea, depression, anxiety, end-stage renal disease, cancer (type), organ transplantation (type)
- vi. Respiratory medication use on admission
- vii. Cardiovascular medication use on admission
- viii. Assessment of in hospital MI treatment: thrombolytics, PCI, CABG
- ix. Diagnosis of ST elevation MI (STEMI) or non-ST elevation MI (NSTEMI)
 - x. Initial post MI ejection fraction from inpatient echocardiogram
 - xi. Length of hospital stay
 - xii. Length of ICU stay
 - xiii. Need for intubation
 - xiv. Cardiogenic shock during hospital stay
 - xv. Discharge cardiovascular medications
 - xvi. Discharge disposition
- b. Phone calls (Option 1 only) and EMR review at 3 and 6 months
 - i. Vital status
 - ii. Date and cause of death if applicable
 - iii. Interval history of hospitalization and primary diagnosis (all events will be captured but hospitalizations for COPD exacerbations, recurrent MI, revascularization, or heart failure will be specifically queried)
 - iv. Interval history of treatment with steroids or antibiotics for exacerbations of COPD
 - v. Beta-blocker use and reason for discontinuation, if applicable Medical records will be collected for all admissions

g) Analytic and Statistical considerations.

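### Admissions already scheduled at index discharge count as primary events, and no listed data item or analysis separates them

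*Combined protocol and SAP*

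**What the plan says.** Section 4.g.b (Analysis plan for Aim 2) sets the primary analysis as a plan to "compare the risk of death or all-cause hospitalization at 6 months" between patients discharged alive on and off beta-blockers. It is a first-event analysis based on "adjusted Kaplan–Meier survival curves that describe the probability remaining alive and out of hospital", with inverse probability of treatment weighting (IPTW) and an adjusted log-rank test. Time starts at discharge, and "Participants will be censored at 6 months post-discharge if no event occurred".

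The nearest secondary outcome is "rates of hospitalization for recurrent MI or revascularization or heart failure", which pools revascularization with two acute events.

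Section 4.f.b says that all hospitalizations are captured with their primary diagnosis, that "hospitalizations for COPD exacerbations, recurrent MI, revascularization, or heart failure will be specifically queried", and that "Medical records will be collected for all admissions". It lists no planned or elective status. On index treatment, section 4.f.a has "Assessment of in hospital MI treatment: thrombolytics, PCI, CABG"; it lists no item for residual coronary disease or an intended staged procedure.

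**The concern.** Section 4.c admits only patients catheterized for AMI, so a second procedure may already be scheduled for some of them when follow-up starts. Three things follow.

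- **Dilution.** The decision to readmit predates any effect of the discharge prescription. Such events, if equally common in both groups, pull the hazard ratio toward 1.
- **Masking.** In a first-event analysis an early planned admission ends follow-up and hides a later unplanned one.
- **Bias.** If planned procedures are more common in one group, they create a difference that is not a drug effect, in either direction. Weighting removes this only if its drivers are measured and included. Staging intent is not a listed item, the named Cox covariates include no revascularization or coronary-extent variable, and the choice of weighting variables is left to be informed by the Aim 1 comparison.

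**Working it through.** **Inputs from section 4.g.c.** Six-month risk of death or re-hospitalization is 25% on beta-blockers and 32.5-37.5% off them; 45-85% are treated; power is 80% and type-I error 5%; the target is 500 discharged alive. Sidedness is not stated; two-sided reproduces Table 1.

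**Reproducing Table 1.** With q the proportion treated, p1 the treated risk and p0 the untreated risk (Schoenfeld):

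- HR = ln(1 − p1) / ln(1 − p0)
- events D = (1.960 + 0.842)² / [q(1 − q)(ln HR)²]
- N = D / [q·p1 + (1 − q)·p0]

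For 25% versus 35% at q = 0.65: HR = 0.2877/0.4308 = 0.668; D = 7.849/(0.2275 × 0.1630) = 211.6; N = 211.6/0.285 = 742.6, against 743 in the table. For 25% versus 37.5% the result is 487.4, against 488. All 44 cells agree to within 0.13%, so the table holds no arithmetic error.

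**Power at 500.** Power = Φ(|ln HR|·√[D·q(1 − q)] − 1.960), with D = 500·[q·p1 + (1 − q)·p0]. For 25% versus 35% at q = 0.65: D = 142.5, and Φ(0.4038 × 5.694 − 1.960) = Φ(0.339) = 63%. For 25% versus 37.5% it is 81%.

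**Reading A: planned admissions come on top of the planning risks.** Add an independent planned risk e, equal in both groups: p becomes 1 − (1 − p)(1 − e). The range of e, 3-10%, is an assumption. At q = 0.65:

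| Planning risks | e | Risks with planned admissions | HR | N for 80% power | Power at 500 |
|---|---|---|---|---|---|
| 25% vs 35% | 0 | 25.0% vs 35.0% | 0.67 | 743 | 63% |
| | 3% | 27.3% vs 37.0% | 0.69 | 816 | 59% |
| | 10% | 32.5% vs 41.5% | 0.73 | 1004 | 51% |
| 25% vs 37.5% | 0 | 25.0% vs 37.5% | 0.61 | 487 | 81% |
| | 3% | 27.3% vs 39.4% | 0.64 | 534 | 77% |
| | 10% | 32.5% vs 43.8% | 0.68 | 652 | 69% |

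**Reading B: the planning risks already include them.** Table 1 then stands for the endpoint as written. Removing planned admissions gives p = 1 − (1 − p)/(1 − e). From 25% versus 35% at q = 0.65:

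- e = 3%: 22.7% versus 33.0%, HR 0.64, power at 500 is 68%.
- e = 10%: 16.7% versus 27.8%, HR 0.56, power at 500 is 80%.

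The gain from 63% is what a death-or-unplanned analysis could recover.

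**Imbalance with no drug effect.** Assume planned admissions of 8% treated and 4% untreated.

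- Common base risk 25%: 31.0% versus 28.0%, HR = ln(0.690)/ln(0.720) = 1.13.
- Common base risk 35%: 40.2% versus 37.6%, HR = ln(0.598)/ln(0.624) = 1.09.
- Imbalance reversed: 0.89 and 0.92.

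These figures treat planned and other events as independent and the hazard ratio as constant over the six months, and take no account of variance added by weighting.

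**The case against.** **The rates are not in the documents.** No planned-readmission rate is given, nor any link between staging and prescribing. This stands: 3-10% and 8% versus 4% illustrate the mechanism and are not estimates.

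**The planning risks may already include these admissions.** A reader might infer that counting planned admissions leaves the study with less power than Table 1 implies. The documents do not establish that. Section 4.g.c frames the risks as death or re-hospitalization, and the causes behind its 25-45% readmission range include revascularization. Under that reading stated power is unchanged, and only efficiency and interpretation are at issue. Nor does dilution sink every planning cell: at 25% versus 37.5% with half treated, adding 3-5% leaves power at 83-81%.

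**All-cause hospitalization is a legitimate endpoint.** It avoids adjudicating causes. This stands, and is a reason to leave the primary alone.

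**The gap is partly covered.** Primary diagnoses and records are gathered for all admissions, so status could be classified later. Index PCI or CABG, prior coronary disease and STEMI or NSTEMI are recorded and could enter the weights. The case report form is not in the documents and may already carry an elective item. What remains is that no listed item or analysis makes the separation, and that classification after results are known invites outcome-driven choices.

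**Conclusion.** The point holds as a gap in data definition and supportive analysis, and is a cheap improvement. As written, an admission scheduled before discharge is a primary event that the discharge prescription could not have caused, and nothing listed separates it.

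Its size is unknown. Under the assumed 3-10%, with 65% treated, either power at 500 falls (63% to 59-51% for 25% versus 35%; 81% to 77-69% for 25% versus 37.5%), or, if the planning risks already include such admissions, the plan forgoes a rise from 63% to 68-80% in the 25% versus 35% case. The documents do not settle which reading applies.

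Two stronger conclusions are not supported. One is that planned admissions will make beta-blockers look harmful: the same imbalance reversed produces apparent benefit, and the documents do not say which way, if either, it runs. The other is that the all-cause primary is wrong and should be replaced.

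**What to change.** Keep death or all-cause hospitalization as the primary outcome, and make two additions.

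1. Add one hospitalization item to the case report form, completed from the records already collected and without reference to beta-blocker status. Mark an admission as planned only if it was scheduled at or before index discharge. Elective admissions arranged later should stay unplanned for this purpose: they post-date exposure and could be affected by it, so removing them could itself introduce bias.
2. Prespecify a supportive IPTW analysis of death or unplanned hospitalization, reported beside the primary. In it a planned admission is not an event, and follow-up continues through it to a later death, unplanned admission or six months.

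The cost is one field, one repeat analysis and some ambiguous classifications where the records do not show when the admission was arranged.

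### The fixed covariate list for the secondary adjusted Cox models leaves out collected markers of MI severity and post-MI treatment, and the unlisted propensity-score variables give no assurance that they are controlled elsewhere

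*Combined protocol and SAP*

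**What the plan says.** Section 4(g)(b) makes weighted Kaplan–Meier curves with an adjusted log-rank test the primary Aim 2 analysis, "while adjusting for the inverse probability of treatment weighting (IPTW) to reduce confounding". It lists no variables for the weights and says only that the Aim 1 comparison of the two discharge groups, made with t-tests and chi-square or Fisher's exact tests, will inform them.

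The Cox models come second: "As secondary analyses, we will use both IPTW and adjusted Cox proportional-hazards models". Their covariates are named: "Adjusted models will also include the covariates of race, sex, baseline age, smoking status, number of hospitalizations for COPD during the previous year", and then "use of supplemental oxygen, presence of ejection fraction <40% at discharge". If group numbers allow, "we will stratify the models by beta-blocker use at the time of admission, presence of asthma, STEMI vs. NSTEMI, and site".

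Section 4(f)(a) collects much more:
- item viii: "Assessment of in hospital MI treatment: thrombolytics, PCI, CABG"
- item xiii: intubation
- item xiv: "Cardiogenic shock during hospital stay"
- item xv: "Discharge cardiovascular medications"
- item v: history of heart failure and, for the kidney, end-stage renal disease only.

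None of these is among the seven covariates or the four stratification factors.

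**The concern.** The exposure is a prescribing decision made at discharge. By then the team knows whether the patient was revascularized, went into shock or was intubated, and which other cardiac drugs are going home with the patient. Each of these can plausibly affect both the choice to prescribe and the six-month risk of death or rehospitalization. If they are left out, the contrast may partly compare milder with more severe infarction, or full with partial post-MI care.

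Section 2 criticises an earlier cohort on this ground: healthier patients may have been the ones given beta-blockers. Section 3 describes the intended adjustment in terms of baseline characteristics and COPD severity, and does not mention MI severity or co-treatment. The seven-item list is the only fixed covariate list in Aim 2, so readers will use it as the check on the weighted result.

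**Working it through.** **1. The plan's own figures.** Inputs from Section 4(g)(c): six-month risk 25% on beta-blockers and 32.5% to 37.5% off; 45% to 85% discharged on beta-blockers; 80% power; 5% type I error; 500 discharged alive.

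Planned hazard ratio = ln(1 − 0.25) / ln(1 − p0):
- p0 = 0.325: 0.732
- p0 = 0.35: 0.668
- p0 = 0.375: 0.612

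Schoenfeld events = (1.960 + 0.842)² / [p(1 − p)(ln HR)²], two-sided. For p0 = 0.35 and p = 0.65 this is 211.6. Dividing by the pooled risk, 0.65 × 0.25 + 0.35 × 0.35 = 0.285, gives 743, the Table 1 entry. All 44 cells of Table 1 reproduce within 3% this way.

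Expected events at N = 500:
- lowest: 500 × (0.85 × 0.25 + 0.15 × 0.325) = 131
- highest: 500 × (0.45 × 0.25 + 0.55 × 0.375) = 159

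**2. How large could the confounding be?** The documents give no prevalence or hazard ratio for the omitted factors, so every input in this step is an assumption. With a true hazard ratio of 1.00, the factor for one omitted binary variable is [1 + (HR − 1)p_on] / [1 + (HR − 1)p_off]. Factors are multiplied as if independent. Intubation is not included.

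| Omitted factor | Modest: on/off, HR | Factor | Larger: on/off, HR | Factor |
|---|---|---|---|---|
| Revascularized | 78/72%, 0.75 | 0.982 | 78/66%, 0.70 | 0.955 |
| Shock | 4/6%, 2.0 | 0.981 | 4/8%, 2.0 | 0.963 |
| Heart failure | 38/40%, 1.5 | 0.992 | 36/40%, 1.5 | 0.983 |
| End-stage renal disease | 4/5%, 1.8 | 0.992 | 4/6%, 1.8 | 0.985 |
| Statin | 95/91%, 0.80 | 0.990 | 95/87%, 0.80 | 0.981 |
| ACE inhibitor/ARB | 72/66%, 0.85 | 0.990 | 72/60%, 0.80 | 0.973 |
| **Product** | | **0.929** | | **0.850** |

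**3. Sensitivity to direction.** Section 2 names heart failure as an established indication for beta-blockers, so it may be commoner in the treated group. At an assumed 45% on and 35% off, its factor becomes 1.225/1.175 = 1.043. The products move to 0.977 and 0.901. Heart failure on its own would then bias against the drug.

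**4. Cross-check by simulation.** This assumed five omitted factors with hazard ratios of 1.3 to 1.8, ejection fraction and STEMI adjusted for, and a true hazard ratio of 1.00. The apparent hazard ratio was 1.00 with no imbalance, then 0.93, 0.87 and 0.82 as imbalance grew. It returned to 1.00 once the five factors were added. A single strong factor (risk ratio 3, prevalence 20% on and 40% off) gives 1.4/1.8 = 0.78, so assumptions more extreme than those in step 2 reach below 0.85.

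**5. Against the planned effect.** ln 0.85 = −0.163, compared with −0.312 (HR 0.732) and −0.491 (HR 0.612): 33% to 52% of the planned log hazard ratio. The standard error, 1/√[d·p(1 − p)], is about 0.16 to 0.24 over the plan's ranges. A spurious 0.85 would raise the two-sided 5% error rate to about 10–17%; a spurious 0.93 would raise it to about 6–7%.

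**The case against.** The Cox models are secondary. The primary analysis is weighted, the weights could include every omitted item, and nothing in the plan excludes them. The word 'also' in the covariate sentence can mean covariates added on top of the weights, in which case the seven items supplement the confounder set and do not define it. Stratification by admission beta-blocker use, asthma, STEMI/NSTEMI and site, together with ejection fraction below 40%, already absorbs part of MI severity, heart failure and local prescribing practice. All participants undergo catheterization, which narrows treatment differences. The step 2 formula ignores the correlation of shock and heart failure with ejection fraction, which is in the model, and so tends to overstate the residual bias. The modest scenario's shift (log hazard ratio about −0.07) is under half the standard error.

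Most of this stands, and it limits the claim. A reader might infer that the plan will credit the benefits of milder infarction and fuller treatment to the beta-blocker. The documents do not support that: they leave open whether the weights carry these factors, the direction is not uniform, and every bias figure rests on assumed inputs.

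The objection does not remove the gap. No section says that the weights will include these items. Whether co-prescribed drugs count among the characteristics compared in Aim 1 is undefined. The stratification is conditional on numbers, and neither it nor ejection fraction captures revascularization, renal failure or other discharge drugs.

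**Conclusion.** The point holds as a risk of residual confounding in the secondary Cox models, and it extends to the primary analysis if the unlisted weights omit the same factors. It is settled by the text that the named items are collected and absent from the covariate list. Size and direction are not settled. In the step 2 and 3 scenarios a true null appears as a hazard ratio of about 0.85 to 0.98, against a planned 0.61 to 0.73; the bias is nil if the factors are balanced or carried by the weights. None of these scenarios alone produces the planned effect, but the larger one is up to about half of it on the log scale. The plan's own sample size figures are unaffected.

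**What to change.** In Section 4(g)(b):
- Name one confounder set, before outcome data are examined, for both the propensity model and the adjusted Cox model: the seven listed items plus in-hospital PCI/CABG, cardiogenic shock, intubation, heart failure history and end-stage renal disease.
- State whether the adjusted Cox model is also weighted.
- Report the hazard ratio with and without the other discharge cardiac drugs (for example statin, ACE inhibitor/ARB and antiplatelet, each yes/no) as a sensitivity analysis. They are decided together with the beta-blocker, so both results are informative.

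All items are already abstracted, so the change is one of wording. The cost is model size. Counting one term for each listed covariate and one for the beta-blocker gives 8. The five additions bring this to 13, or about 10 to 12 events per term (131/13 to 159/13). Three drug terms bring it to 16, or about 8 to 10. Multi-level race, smoking or PCI/CABG terms would tighten this further. The added set should therefore stay short, or enter through the propensity score or a penalised fit.
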